11.1 Choice of analysis data set

Full analysis set: refers to the ideal subject set that is as close as possible to the principle of intentional analysis (the main analysis should include all randomized subjects). This data set is composed of all randomized subjects with the smallest sum It is obtained after a reasonable method is eliminated. Missing data of withdrawn participants is imputed using the multiple imputation method. The number of subjects who evaluated the efficacy at the end point of each group remained the same as that at the beginning of the trial.

Per Protocol Set: In line with the experimental treatment plan, the main variables can be measured, the baseline variables are not missing, and there is no major violation of the experimental plan.

Security set: All subjects who received at least one treatment after randomization.

The main variables were analyzed using the full analysis set and the conforming plan set; the demographics, other baseline characteristics, and other curative effect index analysis were all using the conforming plan set.

11.2 statistical software

SAS 9.4 and graphpad were used for statistical analysis

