4.5 Subject dropping and handling

Criteria for Subject dropping: subjects who have received informed consent and screened qualified to enter the randomized trial, who fail to complete the course of treatment and observation period specified in this program for some reason, are regarded as dropped cases.

Disposal of subjects dropping:

• When the subject falls off, the person in charge of the project will contact the subject as much as possible, ask the reason, record the details, and complete the evaluation project as much as possible by means of door-to-door visits, follow-up appointments, telephone calls, and WeChat.

- If the test case is withdrawn due to needle allergy or fainting or other adverse reactions, and treatment is ineffective, the person in charge of the project will take corresponding measures based on the actual conditions of the subjects.
- Relevant test data are properly kept for the dropped cases and kept in files for subsequent statistics of the full analysis set. There is no need to re-recruit subjects to fill the number of dropped cases.

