4.6 Subject elimination

- Due to the patient's concealment of the condition or other conditions, cases that did not meet the inclusion criteria and met the exclusion criteria were found after inclusion.
- After being included, they refused to participate in the trial and have not yet recorded any clinical data.

Before the statistical analysis of the data, the statistician and the main researcher shall discuss and judge whether the case should be eliminated.

5. Interventions

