7.2.2.2.2 Visual analogue scale (VAS)^{8,9}

A horizontal line 10cm long (or 100mm), one end of the horizontal line indicates no pain (0); the other end indicates the most severe pain imaginable (10); the middle part indicates different degrees of pain. Ask the subjects to draw a vertical line mark at the place closest to their pain level to quantify the intensity of their pain.

no pain worst imaginable pain

Time Frame: Change from Baseline at 1 day, 3 days, 1 week, 2 weeks, 3 weeks and 4 weeks, one-month follow-up after treatment

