9.3 Measures to improve subject compliance

In order to obtain better compliance, make the final summary analysis not less than 80% of the total number of cases entered into the trial, adopt the following measures to improve patient compliance: adhere to the principle of voluntariness, sign patient informed consent; from medical treatment Improve and maintain good patient compliance in terms of quality, treatment environment, medical expenses, etc., to encourage patients to adhere to treatment as much as possible during the study period; pay attention to establishing a good doctor-patient relationship, and explain in detail various examinations, treatments and re-examinations for included cases To obtain the patient's consent and cooperation for the purpose and necessity; record their contact information in detail for follow-up.

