11.4 Statistical analysis of population

Randomized population: all randomized subjects constitute a randomized population.

According to the ITT principle, all randomized subjects will be statistically analyzed.

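### The baseline table and at least ten secondary efficacy outcomes are assigned to the per-protocol set alone, against the protocol's own intention-to-treat statement

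*Protocol*

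**What the plan says.** Section 11.1 defines three sets: full analysis, per protocol and safety. The per-protocol set is described as "In line with the experimental treatment plan, the main variables can be measured, the baseline variables are not missing", with the further condition of no major protocol violation. The section then assigns outcomes to sets:

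- For the primary outcome: "The main variables were analyzed using the full analysis set and the conforming plan set".
- For everything else in baseline and efficacy: "the demographics, other baseline characteristics, and other curative effect index analysis were all using the conforming plan set".

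Only three sets are defined, and the conforming plan set is named beside the full analysis set, so it can only be the per-protocol set.

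Section 11.4 states: "According to the ITT principle, all randomized subjects will be statistically analyzed". It names no endpoint and makes no exception.

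Section 4.5 instructs staff, when a patient drops out, to "complete the evaluation project as much as possible by means of door-to-door visits" and by other forms of contact, and to retain that patient's data for the full analysis set. Section 4.6 adds that, before analysis, "the statistician and the main researcher shall discuss and judge whether the case should be eliminated".

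**The concern.** This is a superiority comparison with sham, and its secondary results should rest on the groups as randomised. Following the treatment plan, having a measurable main variable and avoiding a major violation are all, at least in part, settled after allocation. If exclusions differ between arms and are related to outcome, the secondary differences are biased.

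Different exclusion by arm is plausible here, though not certain. Acupuncturists are unblinded (section 3.3). A patient can be stopped for not tolerating acupuncture or on a doctor's judgement (section 4.4). Only the active arm has skin penetration and current (sections 5.2 and 5.3).

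Three further consequences follow:

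- A per-protocol baseline table cannot show whether the arms were balanced as randomised.
- The primary full-analysis-set result and the secondary results would describe different sets of patients.
- The secondary data that section 4.5 has staff collect from dropped patients have no planned full-analysis-set use. A patient without a measurable week-4 NRS-11 also fails the set definition, so that patient's observed early VAS scores are lost as well.

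**Working it through.** **1. Do the sections conflict?** For baseline data and secondary efficacy, 11.1 gives the per-protocol set only, while 11.4 gives all randomised subjects. Section 4.5 keeps dropped patients' data for the full analysis set, but under 11.1 that set serves only the main variables. No section provides a full-analysis-set analysis of the other outcomes.

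**2. Which outcomes are affected?** The visits come from the time frames in section 7.2.2.

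- VAS, VRS, MPT, PAP, ANPE and ADEPE each have "Change from Baseline at 1 day, 3 days, 1 week, 2 weeks, 3 weeks and 4 weeks, one-month follow-up after treatment", which is 7 visits: 6 × 7 = 42.
- SF-MPQ-2, ZBPI, DAPOS and PGIC each have week 4 and the one-month follow-up: 4 × 2 = 8.
- Total: 42 + 8 = 50 outcome-by-visit comparisons across ten outcomes.
- NRS-11 is listed as both primary and secondary, and 11.1 speaks of main variables in the plural, so its 6 visits other than week 4 are ambiguous. Including them gives 50 + 6 = 56 comparisons across eleven outcomes.

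**3. How many patients?** The plan's own figure first. Section 3.4 gives a difference of 1.2, SD 3.5, 90% power, two-sided 5% error and 20% dropout. With the normal approximation:

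n per arm = 2 × (1.960 + 1.282)² × 3.5² / 1.2² = 178.8, so 179; 179 / 0.8 = 223.75, so 224 per arm and 448 in total.

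The stated 448 is reproduced. Patients absent from the baseline table and secondary comparisons, if all dropouts and nobody else leave the per-protocol set:

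| Share leaving the set | Absent | Remaining |
|---|---|---|
| 10% (assumed) | 448 × 0.10 = 44.8, about 45 | about 403 |
| 20% (planned dropout) | 448 × 0.20 = 89.6, about 90 | about 358 |
| 30% (assumed) | 448 × 0.30 = 134.4, about 134 | about 314 |

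Patients lost after week 4 may stay in the set, and major violators who did not drop out would leave it. The true figure can therefore fall on either side of 90.

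**4. How large could the bias be?** The protocol gives no SDs or exclusion rates for these scales, so the following is illustration only, in SD units, with every input assumed. Let p be the share excluded in an arm and let the gap be the mean of excluded patients minus the mean of retained patients, the same in both arms. Then the retained mean equals the arm mean minus p × gap, and

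bias = (difference in p between arms) × gap.

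With 224 per arm before exclusion and no true effect:

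| Excluded, arm v arm | Gap | Bias | SE | Actual two-sided error at nominal 5% |
|---|---|---|---|---|
| equal | any | 0 | – | 5.0% |
| 17.5% v 22.5% | 0.3 SD | 0.05 × 0.3 = 0.015 SD | √(1/184.8 + 1/173.6) = 0.1057 | 5.2% |
| 15% v 25% | 0.5 SD | 0.10 × 0.5 = 0.05 SD | √(1/190.4 + 1/168.0) = 0.1059 | 7.6% |

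The error rate is Φ(−1.96 + bias/SE) + Φ(−1.96 − bias/SE), with bias/SE about 0.14 and 0.47 in the last two rows.

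**The case against.** The best defence is that 11.4 is a general principle and 11.1 applies it endpoint by endpoint. Section 11.1 itself ties the inclusion of all randomised subjects to the main analysis. That reading softens the contradiction, but it does not rescue the choice: if 11.1 governs, the secondary comparisons with sham are still per-protocol only.

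The other points mostly limit the size of the claim:

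- The 20% is a sample-size allowance, not a forecast of per-protocol exclusions. This stands, and it is why the 90 patients are a scenario.
- Section 9.3 aims to "make the final summary analysis not less than 80% of the total number of cases entered into the trial". That is a retention target and defines no analysis set. It shows only that a loss of up to one fifth was contemplated.
- The inputs to the error-rate illustration are assumed, and two of the three rows show little or no inflation. This stands. A full-analysis-set analysis also relies on imputation where data are missing, and imputation removes bias only if its assumptions hold.
- Section 11.5 does not commit to a separate test at every visit. The counts of 50 and 56 therefore show scope, not harm.
- Section 11.3 plans to report dropouts and eliminations, so unequal losses between arms could be seen. Seeing them does not restore the randomised comparison.

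Leaving analysis sets to an SAP is no answer here, because the protocol fixes the set itself. An SAP would have to repeat 11.1 or contradict it.

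**Conclusion.** The concern holds, and section 11.1 is wrong as written. It gives the baseline table and ten secondary efficacy outcomes (eleven on the wider reading) no full-analysis-set analysis, and it does not agree with 11.4. About 90 of 448 randomised patients would be left out if the planned 20% drop out and all of them leave the per-protocol set.

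The direction and size of any bias cannot be known from the protocol. It is zero if exclusions and outcome gaps are equal between arms, and it grows with the imbalance. The conclusion does not depend on the illustration; it rests on the wording of 11.1 and on a set defined partly by events after randomisation.

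This should be fixed, but it does not threaten the primary result, which has a full-analysis-set analysis. Safety is outside the point, since the restricting sentence covers only baseline and efficacy.

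**What to change.** Replace the last sentence of 11.1 with wording such as:

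> Demographics, baseline characteristics and all efficacy outcomes, primary and secondary, are analysed in the full analysis set with patients as randomised; this is the main analysis. Missing secondary data are handled by a stated method, such as the multiple imputation already planned. The per-protocol set is supportive only.

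Also state whether NRS-11 at visits other than week 4 counts as a main variable. To bring the text fully into line with 11.4, say that elimination under 4.6 removes a case from the per-protocol set, and that any removal from the full analysis set follows a narrow rule fixed before unblinding. This last step goes a little beyond the defect itself, but without it the full analysis set remains open to case-by-case judgement.

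The cost is protocol and SAP wording plus some analysis work: a missing-data method for ten or more outcomes and a supportive per-protocol run. No new data are needed and the sample size does not change. The change should be made before unblinding, so that results cannot influence the choice of set.

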11.3 Content of statistical analysis

The actual number of subjects in the two groups, shedding and elimination cases, demographic and other baseline characteristics, compliance, observation index analysis and safety analysis.

11.4 Statistical analysis of population

Randomized population: all randomized subjects constitute a randomized population.

According to the ITT principle, all randomized subjects will be statistically analyzed.

11.5 Statistical analysis method

The description of the enumeration data will use the number of cases and percentages, and the comparison between groups will use chi-square test, Fisher's exact probability method, Wilcoxon rank sum test, CMH χ^2 test, and WLS covariance. The description of the measurement data will be carried out using the mean \pm standard deviation, median, maximum, and minimum value. Quantitative data conform to a normal distribution with t test (test for homogeneity of variance between groups, with 0.05 as the test level, uneven variance The Satterthwaite method was used for the corrected t test), the Wilcoxon rank sum test and the Wilcoxon signed rank sum test were used for non-normal distribution. The hypothesis test uses a two-sided test uniformly, and the test statistics and the corresponding P value are given. P<0.05 is considered statistically significant, and P<0.01 is considered highly statistically significant.

12. Ethical considerations

Ethical review: This study will follow the relevant regulations of the World Medical Congress "Declaration of Helsinki". Before the start of the study, the clinical study was carried out after the ethics committee approved the trial protocol. If this protocol is revised during the implementation of the clinical trial, it will be submitted to the ethics committee for approval before implementation.

Benefits and risks: The subjects and the society will benefit from this research, including the pain of the subjects will be improved, and the subjects can get the research-related inspection fees and registration fees for free during the research period. Obtain good medical services during the period. At the same time, this study may help more patients in the international community recognize the analgesic effect of electroacupuncture on PHN patients, so as to help other patients with the same disease get rid of pain as soon as possible. Subjects are at risk of possible adverse events due

to acupuncture during the experiment, such as fainting needles, broken needles, local infections or subcutaneous hematomas, etc. Researchers will take corresponding diagnosis and treatment measures according to the condition, and suspend observation when necessary to protect Subject safety.

Recruitment of subjects: Recruiting subjects announcements, WeChat public account tweets, etc., release relevant information \rightarrow sign up for interested persons \rightarrow read research introduction \rightarrow subject screening \rightarrow selection of qualified persons \rightarrow sign informed consent \rightarrow random subjects Grouping \rightarrow baseline evaluation \rightarrow electroacupuncture intervention \rightarrow collecting observation indicators. Please refer to the attachment for the recruitment notice and research brief, and submit it to the ethics committee for review.

Medical treatment and protection of subjects: The investigator is responsible for the medical treatment of the subjects, ensuring that the subjects receive appropriate treatment in the event of adverse events during the trial.

Subject's privacy protection: The subject's personal privacy and data will be protected during the research process, and the subject's personal information will not be disclosed. Only the researchers participating in the clinical trial may have access to the subject's personal medical records. Data processing will adopt the method of "data anonymity", omit the information that can identify the individual of the subject, and will publish it publicly regardless of whether the research results are positive or negative.

Informed consent process: Before each subject is selected for this study, the investigator will give the subject or his agent a complete and comprehensive introduction to the details of the study, including the purpose of the trial, trial procedures, possible benefits and Risks, subjects' rights and obligations, etc., to enable subjects to fully understand and have sufficient time to consider, and to give their consent after satisfactory answers to all questions raised, and to sign written informed consent, and let subjects know that they have The right to withdraw from this study at

any time, and the informed consent will be retained as a clinical study document for future reference. When each patient signs the informed consent form, the doctor will leave his contact number to the patient so that the patient can contact the doctor at any time when his condition changes.

13. Abbreviations

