3.2 Randomization

Eligible patients are randomly allocated in a ratio of 1:1 to the EA or SEA group by a central randomization system (Clinical Research Data Collection and Management System of Jiangsu Province Hospital of Chinese Medicine). Multi-center stratified variable block randomization is used, and the block size of each center is randomly set to 4, 6, and 8. Considering that the number of patients in each stratum fluctuates due to block variation, 21 stratums are preset at random and take the first 7 groups with the number of patients equal to 64 as the final grouping. The randomization sequence is

generated and validated by an independent statistician using R software, and then imported into EDC's central randomization system and kept by an administrator who do not participate in this trial. The central randomization system has set strict personnel permissions, and no one has right to view the randomization scheme except the highestlevel system administrator. After participants meet all the inclusion criteria and complete the baseline assessment, an acupuncturist will log in to the central randomization system to apply for random numbers which will be displayed then, and the patients will receive the corresponding treatment. The Clinical Research Coordinators (CRCs) will be responsible for enrolling participants, obtaining informed consent, and CRF recording.

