3.4 Sample size

According to previous studies, it is anticipated that a difference in primary outcome (NRS-11) between EA group and SEA group is 1.2 and the combined standard deviation of the two groups is 3.5. To achieve 90% statistical power and control the type I error rate below 0.05, we calculated by PASS 15 that a sample of 448 participants (224 participants in each group) will be required to detect a two-sided significant difference between the two groups and compensate for a dropout rate of 20%. All participants are equally distributed among 7 clinical centers, and 64 participants per center will be recruited.

4. Subjects

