4.2 Eligibility criteria

- Meet the diagnostic criteria for PHN;
- Men or women between 45 and 75 years;
- Diagnosed with moderate or higher pain during the screening observation period (daily pain scores of 11-point numeric rating scale (NRS-11) were collected during the observation period, and the average pain score ≥4);
- Did not participate in other ongoing clinical studies;
- Volunteer to participate in the AEEPN trial and sign the informed consent form

(ICF).

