7.2.2 Outcomes

7.2.2.1 primary outcome

11-point numeric rating scale (NRS-11)⁶⁻⁸: Use a scale of 0-10 to represent different degrees of pain: 0 means no pain; 10 means severe pain.

The grading standard of pain degree is: 0: no pain; 1-3: mild pain; 4-6: moderate pain; 7-10: severe pain.

Time Frame: Change from Baseline at 4 weeks

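### Section 11.5 lets an unspecified normality check choose the primary test and leaves baseline NRS-11 (as a covariate) and centre unused; naming one ANCOVA is a free improvement

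*Protocol*

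**What the plan says.** The primary outcome is NRS-11 (section 7.2.2.1: "Use a scale of 0-10 to represent different degrees of pain"), with time frame "Change from Baseline at 4 weeks".

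Section 11.5 does not single out the primary outcome. For quantitative data in general it says "Quantitative data conform to a normal distribution with t test", with a variance pre-test at 0.05 and the Satterthwaite version if variances differ, and "the Wilcoxon rank sum test and the Wilcoxon signed rank sum test were used for non-normal distribution". CMH and WLS covariance methods are listed only for enumeration data.

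Section 3.4 sizes the trial on means: the anticipated "difference in primary outcome (NRS-11) between EA group and SEA group is 1.2" and "the combined standard deviation of the two groups is 3.5". Section 3.2 states that "Multi-center stratified variable block randomization is used", with centre as the stratum, and places the baseline assessment before the random number is requested. Section 4.2 collects daily NRS-11 scores during screening and requires "the average pain score ≥4".

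Section 11.1 applies multiple imputation in the full analysis set and analyses the main variables in both that set and the per-protocol set. Section 10 adds an interim analysis of the primary outcome at 50% of the data.

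**The concern.** Two things in the stated rule could be better at no cost.

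1. **The data choose the primary test.** A t test compares mean change; a Wilcoxon test compares ranks and does not target the mean difference of 1.2 on which the trial is sized. Section 11.5 gives a level for the variance pre-test but neither a method nor a level for the normality check, so the analyst's choice of check can decide the primary test. The check could also give different answers across imputed data sets, analysis sets, or interim and final data. Wilcoxon results do not pool over imputations as simply as a regression coefficient does.

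2. **Available information is left out of the model.** Baseline NRS-11 enters only through the subtraction in the change score, which fixes its coefficient at 1 instead of estimating it. Centre is balanced by design and then ignored. Both variables will already be in the database.

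At stake are a primary test and effect measure fixed in advance, and a little precision.

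**Working it through.** **Inputs from the protocol.** Difference 1.2, SD 3.5, two-sided alpha 0.05, power 90%, dropout 20%, 224 per arm (section 3.4); seven centres (sections 3.1 and 3.4). Section 3.4 does not say whether 3.5 is the SD of the change or of the week-4 score.

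**Assumptions (not in the protocol).** Baseline SD (sb) 1.25 to 2.0; baseline to week-4 correlation (r) 0.3 to 0.5; centre share of variance 2 to 10%; whole-number scores; the score distributions in the simulations.

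**Step 1: reproduce the sample size.** n per arm = 2 × (1.960 + 1.282)² × 3.5² / 1.2² = 2 × 10.507 × 12.25 / 1.44 = 178.8, so 179. Then 179 / 0.8 = 223.75, so 224 per arm and 448 in total. The stated figure reproduces as an unadjusted comparison of two means. Its power at 179 per arm is 0.899 by the noncentral t distribution (0.900 by the normal approximation).

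**Step 2: power with baseline as covariate, 3.5 read as the SD of change.** Solve s4² − 2·r·sb·s4 + sb² = 12.25 for the week-4 SD s4. The residual SD is s4·√(1 − r²). Power is at 179 per arm.

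| sb | r | s4 | residual SD | power |
|---|---|---|---|---|
| 1.25 | 0.3 | 3.67 | 3.50 | 0.899 |
| 1.25 | 0.5 | 3.95 | 3.42 | 0.911 |
| 1.5 | 0.3 | 3.64 | 3.48 | 0.903 |
| 1.5 | 0.5 | 4.00 | 3.46 | 0.905 |
| 2.0 | 0.3 | 3.53 | 3.37 | 0.919 |
| 2.0 | 0.5 | 4.04 | 3.50 | 0.899 |

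The gain over 0.899 is 0 to 2 percentage points. If 3.5 is instead the week-4 SD, the change SD is √(12.25 + sb² − 7·r·sb) and the residual SD is 3.5·√(1 − r²). The gain is then 0.1 points (for example sb 1.5, r 0.5: 0.961 to 0.962) to about 2 points (sb 2.0, r 0.3: 0.903 to 0.924).

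**Step 3: add centre.** Simulation with 7 centres × 26 per arm, change SD 3.5, 8,000 runs. Cells show power unadjusted / centre / baseline and centre.

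| centre share | sb 1.25, r 0.3 | sb 1.5, r 0.5 | sb 2.0, r 0.3 |
|---|---|---|---|
| 2% | 0.909 / 0.910 / 0.910 | 0.910 / 0.912 / 0.916 | 0.908 / 0.912 / 0.930 |
| 5% | 0.912 / 0.918 / 0.918 | 0.912 / 0.918 / 0.927 | 0.907 / 0.914 / 0.934 |
| 10% | 0.918 / 0.932 / 0.930 | 0.918 / 0.931 / 0.934 | 0.919 / 0.932 / 0.947 |

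The joint gain is at most 2.8 points (0.919 to 0.947). Simulation error on each power is about √(0.91 × 0.09 / 8000) = 0.003.

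**Step 4: type I error.** Unadjusted against baseline plus centre (10,000 runs): 0.050 / 0.052, 0.043 / 0.049 and 0.042 / 0.053 at centre shares of 2, 5 and 10%. For the two-step rule itself (Shapiro-Wilk, then t or Wilcoxon; 2,000 runs per setting) the range was 0.042 to 0.062, against 0.044 to 0.060 for ANCOVA. The simulation error there is about √(0.05 × 0.95 / 2000) = 0.005. There is no material inflation.

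**Step 5: which test the rule selects.** Whole-number 0 to 10 scores, entry at 4 or more, true mean difference 1.2:

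- Shapiro-Wilk at 0.05 in either arm selected Wilcoxon in 100% of runs in all 13 settings, with change SDs from 1.8 to 3.7.
- A rule of absolute skewness or excess kurtosis above 1 selected it in 0 to 0.4% of runs at SD 1.8 to 2.6, 56% at 3.16 and 99% at 3.49. A separate simulation with another score distribution gave 48% at SD 3.52, so this result depends on the assumed shape even near the protocol's 3.5.
- The t test and Wilcoxon disagreed on significance in 0 to 4% of runs.
- Switching of test between half and full data was 0 to 1.4%, and nil from SD 3.16 up. With a 7-day average as baseline it was 12 to 41% at SD 1.8 to 2.65, 0.2% at 3.19 and nil at 3.51.

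**The case against.** **This is a matter for the statistical analysis plan.** Covariates and the final model are commonly left there, and their mere absence would be no point. But section 11.5 is not silent: it writes a data-dependent choice of test as the only method for quantitative outcomes. An analysis plan naming one ANCOVA would have to depart from it.

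**Baseline is already used.** True: the outcome is a change score. Only its use as a covariate is missing, and the unadjusted comparison of change is valid.

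**The gain may be nil.** Also true: at baseline SD 2.0 and r 0.5 it is zero, and the protocol gives neither input. A reader might infer much more from the textbook variance ratio (1 + r)/2, which gives power of 0.963 at r 0.5 and would suggest a smaller trial. That ratio needs equal variances at baseline and week 4. With a change SD of 3.5 and r 0.5 it implies a baseline SD of 3.5, whereas scores confined to 4 to 10 cannot have an SD above (10 − 4)/2 = 3. No reduction in sample size is supported.

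**Wilcoxon is not certain.** The protocol states neither whole-number scores nor a formal normality test. Nor would mean information be lost: section 11.5 describes quantitative data by mean and SD whichever test is used, and it plans no rank-based shift estimate that could be faulted.

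**Baseline timing is contradictory.** Section 3.2 puts the baseline assessment before randomisation, while the recruitment flow in section 12 lists it after grouping. The daily screening scores of section 4.2 precede randomisation in any case, so a valid covariate exists, but it must be defined.

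**Conclusion.** The point stands as an improvement worth considering, not as an error that endangers the trial.

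- **Firm, from the text alone:** an unspecified normality check chooses the primary test; the rank branch does not match the mean-difference sizing; baseline as a covariate and centre are unused.
- **Conditional:** Wilcoxon will almost always be chosen if scores are whole numbers and a formal check such as Shapiro-Wilk is applied. With a moment-based check the choice depends on the score distribution.
- **Small:** power 0.899 unadjusted against 0.899 to 0.919 with baseline, and up to 2.8 points gained with baseline and centre together, all under assumed SDs, correlations and centre shares.

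A reader might infer that the two-step rule inflates type I error, that the trial falls short of 90% power, or that interim and final analyses would use different tests. The checks support neither of the first two. Switching appeared mainly with an averaged baseline at change SDs well below 3.5, and not near 3.5.

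**What to change.** In section 11.5, for the primary outcome:

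1. Drop the normality check and the variance pre-test as selectors of the test.
2. Name one primary analysis: ANCOVA of week-4 NRS-11 change on treatment, baseline NRS-11 and centre, pooled over the imputations, reporting the adjusted mean difference with its 95% confidence interval.
3. Use the same model at the interim analysis and in both analysis sets.
4. Keep Wilcoxon as a sensitivity analysis.
5. Define baseline as a pre-randomisation score, say whether it is a single score or the screening average, and reconcile the order of events in section 12 with section 3.2.

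The cost is protocol or analysis-plan wording and a few lines of SAS, with no new data and no extra patients. The model spends seven degrees of freedom (one for baseline, six for centre). The change should be made before any unblinded look at the data, including the interim analysis.
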